10.5 Subgroup Analysis

The primary and key secondary efficacy endpoints along with the FACIT-F FS score, LIC/ICT response and 6-minute walk test will also be summarized for the following subgroups:

1. Geographic region:
 - North America and Europe
 - Middle East
 - Asia-Pacific
2. Age:
 - ≤ 32 years
 - > 32 years
3. Splenectomy:
 - Y
 - N
4. Sex:
 - Male
 - Female
5. Beta-Thalassemia diagnosis:
 - Beta-Thalassemia

- Hemoglobin E/Beta-Thalassemia
 - Beta-Thalassemia combined with Alpha-Thalassemia;
6. Baseline liver iron content
 - < 3 mg/g dry weight
 - ≥ 3 - ≤ 5 mg/g dry weight
 - > 5 - ≤ 7 mg/g dry weight
 - > 7 - ≤ 15 mg/g dry weight
 - > 15 mg/g dry weight
 7. Mean baseline Hb (mean of at least 2 Hb values by Central Lab during the 28 days screening period) (g/dL)
 - ≥ 8.5 g/dL
 - < 8.5 g/dL
 8. Baseline NTDT-PRO T/W Score
 - a. ≥ 3 points
 - b. < 3 points
 9. Baseline 6MWT
 - a. ≤ 450 meters
 - b. > 450 meters
 10. Baseline FACIT-F FS Score
 - a. ≥ 43
 - b. < 43

A forest plot showing the odds ratios, 95% CI and p-value for the overall result and the results in each subgroup will be constructed for primary and key secondary endpoints.

10.6 Handling of Missing Data or Dropouts

10.6.1 Missing Data for non-QoL Assessment

In order to assess the robustness of the findings on the primary and key secondary endpoints of hemoglobin response and change from baseline, the missing values will be imputed as follows:

- For binary responder/non-responder values, the non-responder imputation (NRI) method is used for primary analysis. The NRI method classifies all subjects with missing data as non-

responders. The supportive/sensitivity analysis will include the complete case analysis. The complete case analysis excludes all subjects with missing data.

Tipping point analysis may be conducted for the primary efficacy endpoint if necessary. Different number of responders between luspatercept and placebo will be assessed until the study conclusion is changed. Each imputed value is initially imputed as a non-responder. The imputed values in the luspatercept group will remain as non-responders while the imputed values in the placebo group are replaced as a responder one at a time, therefore changing the number of responders between groups. Once all imputed values in the placebo group have been replaced with responder values, one of the imputed values in the luspatercept group is replaced with a responder while all the imputed values in the placebo group are reset to all non-responders. This process of changing each imputed non-responder to a responder one at a time continues until all the imputed values in the luspatercept and placebo groups are changed to responders.

In this way, every pair of imputations between the placebo and luspatercept groups will be assessed similarly, creating a matrix of all possible missing patterns. At each iteration, the statistical analysis is assessed to result in a significant or non-significant p-value, and the result of the analysis is recorded. A table will be provided to identify at what point to which the difference in responder status causes a directional shift in the study result.

- For continuous values, the complete case analysis is the primary analysis. The supportive/sensitivity analysis will use the postbaseline mean imputation, the baseline imputation or multiple imputation (MI) method.

In the case of any missing data for hemoglobin and LIC from MRI, imputation will be applied for each section. The imputation logic for missing LIC value is stated in Section 10.4.10: the value of LIC will be either the value collected from eCRF or the value derived from T2*, R2* or R2 parameters depending on which techniques and software were used for MRI LIC data acquisition.

10.6.2 Missing Data for QoL Assessment

For continuous and categorical QoL assessments, the complete case analysis is used for the primary analysis. For the key secondary endpoint, NTDT-PRO T/W domain score at Week 13-24, the supportive/sensitivity analysis will use the postbaseline mean imputation, the baseline imputation or multiple imputation (MI) methods to assess the robustness of the primary result.

To assess the extent of missing data at each assessment visit by treatment group, compliance rates for the NTDT-PRO, FACIT-F, and SF-36 assessments at each scheduled visit will be provided. The compliance rate for each assessment at each visit is defined as follows:

- NTDT-PRO: The number of subjects with at least half of 6 weekly item scores for that week being non-missing (i.e., ≥ 3 items) divided by the number of ITT subjects who are still expected to provide PRO assessment at that time point.
- FACIT-F: The number of subjects with at least 80% of the 40 items (i.e., ≥ 32 items) for that visit being completed divided by the number of ITT subjects who are still expected to provide FACIT-F assessment at that time point.
- SF-36: The number of subjects with at least 50% of the 36 items (i.e., ≥ 18 items) for that visit being completed divided by the number of ITT subjects who are still expected to provide SF-36 assessment at that time point.

11 SAFETY ANALYSIS

The purpose of this section is to define the safety parameters for the study. All summaries of safety data will be conducted using the safety population. The safety analysis includes adverse events (AEs), clinical laboratory tests, vital signs, electrocardiogram (ECG), echocardiography, erythropoietin, left ventricular ejection fraction (LVEF), and antidrug antibody (ADA) testing. In addition, pregnancy test and menstrual status assessments will be provided for female subjects.

If not otherwise specified (for example, adverse events), safety summaries will use all collected records.

11.1 Adverse Events

Adverse events will be analyzed in terms of treatment-emergent adverse events (TEAEs) which are defined as any AEs that begin or worsen on or after the start of study drug through 63 days after the last dose of IP (i.e., AE start date on or after the first dose date and within last dose date + 63). In addition, an AE that occurs beyond this timeframe and that is assessed by the investigator as possibly related (suspected) to study drug will be considered as treatment-emergent.

All AEs will be coded using the Medical Dictionary for Regulatory Affairs® (MedDRA) dictionary. The incidence of TEAEs will be summarized by MedDRA system organ class (SOC) and preferred term (PT). The AE tables will be sorted by SOC and PT (within SOC) in descending frequency within the luspatercept group. If a subject experiences multiple AEs under the same PT (or SOC), then the subject will be counted only once for that PT (or SOC).

The intensity of AEs will be graded 1 to 5 according to the National Cancer Institute Common Terminology Criteria for Adverse Events (CTCAE) Version 4.0. If a subject experience the same AE more than once with different toxicity grades, then the event with the highest grade will be tabulated in “by grade” tables. In addition, AEs with a missing intensity will be presented in the summary table as an intensity category of “Missing” only if the same event category has no other valid grades.

Tables summarizing the incidence of TEAEs will be generated for each of the following by treatment group (if not otherwise specified, the summary is by SOC and PT):

- TEAEs;
- TEAEs by SOC only;
- Treatment-related TEAEs;
- Serious TEAE;
- Treatment-related serious TEAEs;
- TEAEs by CTCAE maximum severity
- Treatment-related TEAEs by CTCAE maximum severity
- TEAE with CTCAE Grade ≥ 3 ;

- Treatment-related TEAE with CTCAE Grade ≥ 3 ;
- TEAEs leading to study drug discontinuation;
- Treatment-related TEAEs leading to study drug discontinuation;
- TEAEs leading to study drug dose reduction;
- Treatment-related TEAEs leading to study drug dose reduction;
- TEAEs leading to death;
- Treatment-related TEAEs leading to death;
- Most frequent TEAEs by PT ($\geq 5\%$ in PT frequency of all subjects or subjects from any treatment group);
- Most frequent TEAEs by SOC ($\geq 5\%$ in SOC frequency of all subjects);
- Most frequent TEAEs by SOC and high level term (HLT) ($\geq 5\%$ in HLT frequency of all subjects);
- TEAEs by Age group (≤ 32 years, > 32 years);
- TEAEs by Age group (≤ 32 years, $32-\leq 50$ years, > 50 years);
- TEAEs by Gender (male and female);
- TEAEs by Splenectomy status (Yes/No);
- TEAEs by ADA status (positive preexisting, positive treatment-emergent, negative);
- TEAE by preferred term for QTC Prolongation and Atrial Fibrillation events;
- All death by cause of death;

Listings for AEs, SAE, and AEs leading to drug discontinuation will be presented separately. Treatment-emergent AEs will be flagged in the listings. A death listing will be provided for all death events.

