4.3. Stratification, Randomization, and Blinding

Subjects will be randomized to receive luspatercept or placebo at a 2:1 ratio. Randomization will be accomplished by an IRT to ensure timely registration and randomization. A stratified block randomization schedule will be implemented. Randomization will be stratified by:

- Baseline hemoglobin level
 - a. ≥ 8.5 g/dL
 - b. < 8.5 g/dL
- Baseline NTDT-PRO T/W score
 - a. ≥ 3 points
 - b. < 3 points

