4.4. Sample Size Determination

Based on the assumption of targeted primary endpoint response rates of at least 50% in the luspatercept group and 10% for the placebo group, and 2:1 randomization, a total sample size of

150 (100 in the luspatercept group, 50 in the placebo group) will have at least 99% power to detect the difference between the 2 groups with a 2-sided alpha of 0.05 and assumed 10% dropout rate.

For NTDT-PRO T/W domain scores, assume the mean change from baseline scores at Week 24 are 1.2 and 0.5 for luspatercept and placebo group, respectively, with a common standard deviation of 1.2, the statistical power will be 91%.

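### The frequent-TEAE table by SOC and high level term applies its 5% cut-off to both arms pooled, so at 100:50 a grouped event in 5–7% of luspatercept and no placebo subjects is left out of it, although the preferred-term table's rule would show it

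*SAP*

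**What the plan says.** SAP 11.1 (Adverse Events) lists TEAE tables by treatment group. Three show only the more frequent events, each with a 5% threshold but not with the same denominator:

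- by PT: "in PT frequency of all subjects or subjects from any treatment group"
- by SOC: "in SOC frequency of all subjects"
- by SOC and HLT: "in HLT frequency of all subjects"

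The arm-specific clause stands in the first and is missing from the other two. No reason is given.

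The same list also plans TEAEs by SOC and PT, and TEAEs by SOC alone, with no stated frequency cut-off, and the section ends with AE listings. No other HLT table appears.

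On the denominators, SAP 11 states: "All summaries of safety data will be conducted using the safety population". SAP 4.3 states: "Subjects will be randomized to receive luspatercept or placebo at a 2:1 ratio". SAP 4.4 plans 100 and 50 subjects.

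**The concern.** These tables are laid out by arm so that a reader can compare the arms. A pooled threshold averages in the placebo subjects, so an event confined to luspatercept must be commoner on luspatercept than 5% before it qualifies. The PT table avoids this; the HLT table does not.

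The HLT level matters because it is the only general grouping, not chosen in advance by topic, planned between SOC and PT. If an effect is spread over several related PTs, each under 5% in both arms, the frequent-PT table will not show it and the HLT table is where it would show as one count. SAP 11.1 counts a subject once per PT or SOC, so PT counts cannot simply be added: a subject with two PTs in the same HLT would be counted twice. A reader would have to rebuild the HLT count from subject-level data.

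**Working it through.** **Inputs.** The 5% thresholds come from SAP 11.1, the 2:1 allocation from SAP 4.3, and the 100 and 50 subjects from SAP 4.4. The safety population is taken as the planned 100:50, which assumes nearly all randomized subjects are dosed. A 90:45 case shows the range.

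**The plan's own figure.** The documents give no figure for the effect of the cut-off. The only stated figure that carries the arm sizes is the power of at least 99% for "response rates of at least 50% in the luspatercept group and 10% for the placebo group", with a "2-sided alpha of 0.05 and assumed 10% dropout rate". With the two-proportion normal approximation and pooled null variance:

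- Pooled proportion = (50 + 5)/150 = 0.3667.
- Null SE = √(0.3667 × 0.6333 × (1/100 + 1/50)) = 0.0835.
- Alternative SE = √(0.25/100 + 0.09/50) = 0.0656.
- Power = Φ((0.40 − 1.96 × 0.0835)/0.0656) = 0.9998.

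After 10% dropout (90:45) it is 0.9995. The stated figure reproduces, so the arm sizes can be used.

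**The two rules.** With x cases on luspatercept and y on placebo:

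- HLT rule: show if (x + y)/150 ≥ 5%. Since 0.05 × 150 = 7.5, this needs x + y ≥ 8.
- PT rule: show if (x + y)/150 ≥ 5%, or x/100 ≥ 5%, or y/50 ≥ 5%. The pooled rate is a weighted average of the two arm rates, so it cannot reach 5% unless at least one arm does. The PT rule is therefore in effect an any-arm rule.

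**Luspatercept counts that the PT rule shows, under the HLT rule (100:50):**

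| Placebo cases | Omitted | Largest omitted | First shown |
|---|---|---|---|
| 0 | 5, 6, 7 (3.33%, 4.00%, 4.67% pooled) | 7% vs 0% | 8/150 = 5.33% |
| 1 (2%) | 5, 6 | 6% vs 2%, 7/150 = 4.67% | 7 + 1 = 8 |
| 2 (4%) | 5 | 5% vs 4%, 7/150 = 4.67% | 6 + 2 = 8 |
| 3 (6%) | none | – | 5 + 3 = 8 |

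With no placebo cases and exact 2:1 allocation, the algebraic limit is 0.05 × 150/100 = 7.5% on luspatercept, so 7% is the largest whole-subject rate omitted.

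**Smaller safety population (assumption), 90:45.** The threshold is 0.05 × 135 = 6.75, so 7 cases. With none on placebo, 6/90 = 6.7% is omitted (6/135 = 4.44%) and 7/90 = 7.8% is shown (7/135 = 5.19%). The pattern does not depend on the exact arm sizes.

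**Opposite direction.** A placebo-only HLT is omitted up to 7/50 = 14% under the pooled rule. Under the PT rule it is shown from 3/50 = 6%.

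**How often.** If the true placebo rate were exactly 0%, the chance of 5 to 7 luspatercept cases among 100 is 0.436, 0.472, 0.436 and 0.357 at true luspatercept rates of 5%, 6%, 7% and 8%. The documents give no placebo rate for any HLT, so these are best-case conditions for the omission, not expected frequencies.

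**The case against.** The strongest reply is that nothing disappears from the safety report. The component PTs are shown by arm, sorted by frequency on luspatercept, in the SOC/PT tables without a stated cut-off. Serious, related, Grade 3 or higher, discontinuation, dose-reduction and fatal TEAEs have their own tables, and the listings follow. At SOC level the table by SOC alone backs up the pooled one. All of this stands. A reader might infer that active-only events are hidden or dropped from reporting; the documents do not support that. Only a row of one table is missing.

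A reader might also infer that the HLT table is the only place where related PTs are pooled. It is not. SAP 11.3 plans a summary for the embolic and thrombotic events SMQ, and SAP 11.2 plans summaries for malignancy and premalignant conditions. Those topics are named in advance, so the narrower statement holds: HLT is the only general grouping between SOC and PT.

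Nor does it follow that such an event would appear in no frequent-event table. Every subject in an HLT is also in its SOC. With 7 in the HLT, one further subject in either arm with another event in that SOC brings the SOC to 8 of 150 and into the frequent-SOC table.

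Finally, the 36–47% figures could be read as the chance of missing a safety signal. They are chances of a missing display row, and only at exactly 0% on placebo.

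One may add that a 5% threshold is a display convention and that the tables need not share one rule. That is fair, but neighbouring entries in one list differ without a stated reason, and the difference falls where no other planned table gives the same count.

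**Conclusion.** The inconsistency is real and small. At the planned 100:50, the HLT table leaves out an HLT seen in 5–7% of luspatercept and 0% of placebo subjects, up to 6% with one placebo case and 5% with two; the PT rule would show each of these. The loss is the de-duplicated HLT count by arm, not the underlying events.

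This rests on a safety population close to 100:50 (at 90:45 the largest omitted rate with no placebo cases is 6.7%) and on HLT counts being one per subject, as SAP 11.1 states for PT and SOC. Severity is minor: the tables are descriptive, and no test, estimate or efficacy conclusion changes.

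**What to change.** In SAP 11.1, give the SOC/HLT table the PT table's denominator: 5% "in PT frequency of all subjects or subjects from any treatment group", with HLT in place of PT. Make the same change to the frequent-SOC table for consistency, although the SOC table without a cut-off already gives that information.

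The cost is one phrase per entry and a few more rows. Some of these will be driven by placebo, since 3 of 50 subjects is enough to admit a term.

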11.2 Adverse Events of Special Interest

The following adverse events are of special interest:

- Malignancy
- Premalignant Conditions.

An AESI summary by PT terms will be provided for TEAEs by treatment group. A listing for AESI will be provided as support.

To evaluate the timing of AESI onset, descriptive statistics will be provided for time to first AESI occurrence after treatment by treatment group. A listing for AESI will be provided as support.

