3.1.2. Double-blind Treatment Period

Subjects will enter the Double-blind Treatment Period (DBTP) once they have completed the required assessments in the Screening Period and been randomized via the IRT system, as detailed in [Section 7.3](#). The DBTP will begin on Dose 1 Day 1 and will end when all subjects have completed 48 weeks of treatment or have discontinued earlier. At that time, the study will be unblinded.

Subject randomization will occur via the IRT system and Dose 1 Day 1 should be scheduled within 3 days of randomization (can be on the same day as randomization).

Eligible subjects will be randomized at a ratio of 2:1, luspatercept versus placebo, at a starting dose level of 1.0 mg/kg administered by subcutaneous (SC) injection once every 3 weeks. The maximum total dose per administration is 120 mg.

Best supportive care is allowed in both the luspatercept and placebo groups. This will include RBC transfusions, iron-chelating agents, use of antibiotic therapy, antiviral and antifungal therapy, nutritional support as needed, and other medications that are not prohibited (see Section 8.2), thus minimizing the safety risk to patients. Please, also refer to Section 8.1.2 for concomitant medication for anemia, Section 8.1.3 for concomitant iron chelation therapy use and Section 8.1.4 for concomitant RBC transfusions.

Study visits and serial measurements of safety and efficacy parameters will be performed as described in Table 3, Table of Events.

After the study is unblinded, and after DMC's recommendation:

- Subjects who received placebo and have been assessed as per protocol at least up to 48 weeks after the first dose of IP (even if the IP is discontinued before complete 48 weeks of treatment), may access the Open Label Period (OLP) to receive luspatercept for a maximum 15 months before moving to the rollover protocol for longer treatment.
- Subjects receiving luspatercept may continue their treatment in the OLP for maximum 15 months before moving to the rollover protocol for longer treatment (ie, 5 years from Dose 1 in the DBTP, or until treatment discontinuation, whichever occurs later).
- Subjects who received luspatercept and discontinued the IP in the DBTP may continue and/or complete the PTFP of 5 years from first dose of IP, or 3 years from last dose (whichever occurs later), to complete the Post-treatment Follow-up Period under the rollover protocol in this study until the of End of Trial (see Section 3.3).

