5. GENERAL STATISTICAL CONSIDERATIONS

5.1. Reporting Conventions

Summary tables, listings, figures and any supportive SAS outputs will include a “footer” of explanatory notes that will indicate, at a minimum, the following:

- Program source (e.g., SAS program name, including the path, that generates the output) and
- Data extraction date (e.g., the database lock date, run date)

The purpose of the data extraction date is to link the output to a final database, either active or archived, that is write-protected for replication and future reference. An output date will also appear on each output page and will indicate the date the output was generated by the analysis program.

The following reporting conventions apply generally to tables, listings, and figures:

- Data from all study centers will be combined for analysis;
- The randomization stratification variables used in the analyses will be derived based on the electronic case report form (eCRF) data.
- All statistical tests of the treatment effect will preserve a significance level of 0.050 for 2-sided tests. Testing of interactions will be performed at the 0.100 significance level, unless specified otherwise;
- P-values will be rounded to 4 decimal places. P-values that round to 0.0000 will be presented as ‘<0.0001’ and p-values that round to 1.000 will be presented as ‘>0.9999’;
- Confidence intervals (CIs) will be presented as 2-sided 95% CIs unless specified differently in specific analysis;
- Summary statistics will consist of the number and percentage of subjects in each treatment group for discrete variables, and the sample size, mean, median, Standard Deviation (SD), Q1, Q3, minimum, and maximum for continuous variables;
- All mean, median, Q1, and Q3 values will be formatted to one more decimal place than the measured value. Standard deviation values will be formatted to two more decimal places than the measured value; Minimum and maximum values will be presented to the same number of decimal places as the measured value.
- All percentages will be rounded to one decimal place. The number and percentage of responses will be presented in the form XX (XX.X%), where the percentage is in the parentheses; when the number of a response is zero, percentage will not be presented for that response;
- All listings will be sorted for presentation in order of treatment group, study center, subject, and date of procedure or event if not otherwise specified;

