 - c. Average of all Hb measurements in Weeks 14-25 (Day 93 to Day 176) if Weeks 14-25 has ≥ 3 Hb measurements
 - d. When the number of Hb measurements is less than 3 among Weeks 13-24, Weeks 12-23, and Weeks 14-25, then choose the largest number of Hb measurements in the following order as Hb at Week 13-24:
 - 1) Hb in Week 13-24
 - 2) Hb in Week 12-23

- 3) Hb in Week 14-25
 - e. Otherwise, missing
 - Weeks 37 - 48 interval: Same rule as Week 13-24 interval
- The calculation of weekly NTDT-PRO scores is detailed in Section 18.3.1. The 12-week interval score is obtained by averaging all the weekly scores (at least one non-missing) in these 12 weeks. If all the weekly scores in these 12 weeks are missing, the 12-week interval score is then declared missing.

This SAP addresses efficacy and safety endpoints during the double-blinded treatment period (including the initial 48-week treatment period for all subjects and the long-term treatment period for early enrolled subjects). The database will be locked upon all subjects completed 48 weeks of the double-blind treatment period or discontinued before reaching 48 weeks. All the data collected up to data cutoff date will be used for summary. Data selection rules will be applied in each summary panel as needed, please refer to individual part for details.

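### The by-arm malignancy and premalignancy table in SAP 11.2 counts treatment-emergent events only, so a late event judged unrelated is listed but not tabulated (minor, cheap to fix)

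*SAP*

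**What the plan says.** - **AESI table.** SAP 11.2 names two AESIs, malignancy and premalignant conditions, and states "An AESI summary by PT terms will be provided for TEAEs by treatment group".
- **TEAE window.** SAP 11.1 defines TEAEs as "any AEs that begin or worsen on or after the start of study drug through 63 days after the last dose of IP". A later event enters only if the investigator suspects a relation to study drug.
- **Collection.** Protocol 10.1 and 10.5.3 require every new malignancy or premalignant lesion to be reported regardless of causality, to the later of 5 years from first dose or 3 years from last dose. Protocol 6.4 follows subjects who stop treatment early until unblinding. Footnote 13 of Table 3 asks for a malignancy assessment at least every 24 weeks.
- **Listings.** SAP 11.1 and 11.2 provide AE, SAE and AESI listings. SAP 5.1 adds "All listings will be sorted for presentation in order of treatment group", and SAP 11.1 adds "Treatment-emergent AEs will be flagged in the listings", so the listings also hold events that are not treatment-emergent.
- **Timing of onset.** SAP 11.2 also says "descriptive statistics will be provided for time to first AESI occurrence after treatment by treatment group". It does not state whether this uses TEAEs or all events.

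**The concern.** For these events the protocol takes the investigator's causality opinion out of collection. The AESI table brings it back after day 63: two late malignancies that differ only in that opinion are treated differently, one counted and one not. Much of the value of a by-arm count in a randomized, blinded trial is that it does not rest on such individual opinions.

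The cutoff matters too. SAP 5.1 says "The database will be locked upon all subjects completed 48 weeks of the double-blind treatment period or discontinued before reaching 48 weeks". After unblinding, Protocol 3.1.2 says that subjects who received placebo "may access the Open Label Period (OLP) to receive luspatercept for a maximum 15 months". The final study report (Protocol 9.9.2) covers safety again, but this SAP's cutoff is the last one before placebo subjects can cross over. A reader who wants the randomized comparison of all collected malignancies at that point would have to count the late ones from a listing.

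**Working it through.** **1. Does any other planned output count these events?** The plan states no figure here to reproduce, so the passages are set side by side.
- SAP 11 lets safety summaries use all collected records unless otherwise specified, and gives adverse events as the example of an exception.
- The AE incidence tables in SAP 11.1 are TEAE-based, apart from the table of all deaths by cause. A fatal late case would be seen there, although that is not an AESI table.
- The listings show the event by arm but give no n (%).
- Time to first AESI is not an incidence table. By the convention in SAP 5.1 it would carry "the sample size, mean, median, Standard Deviation (SD), Q1, Q3, minimum, and maximum for continuous variables". On an all-events reading its n could include a late case. On the TEAE reading, which SAP 11.1 makes the natural one, it would not.

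The 11.2 table is thus the only AESI incidence table in the SAP text available, and it omits the late, non-suspected event.

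**2. Who is affected?** 63 days = 63/7 = 9 weeks. With follow-up of F weeks at cutoff and last dose at week L, the time outside the window is F − L − 9 weeks, or zero if negative. Unblinding comes 48 weeks after the last subject's first dose (Protocol Figure 7, note c), so F = 48 applies to the last subject enrolled and earlier subjects can have more. F = 72 is an illustration.

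| F | L | Weeks outside window | Days |
|---|---|---|---|
| 48 | 39 or later | 0 | 0 |
| 48 | 24 | 15 | 105 (31% of 336) |
| 48 | 12 | 27 | 189 (56% of 336) |
| 72 | 24 | 39 | 273 |
| 72 | 12 | 51 | 357 |

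**3. How many events?** The documents give no event rate, stopping pattern or actual follow-up. Assumptions: 15 of 150 subjects stop (10%, borrowed from the drop-out allowance in Protocol 9.3), all at Week 12 or all at Week 24, and all stay in follow-up; the malignancy or premalignancy rate is 0.5 to 2 per 100 person-years.

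Person-years outside the window = 15 × weeks × 7 / 365.25.
- F = 48: 15 × 15 × 7 / 365.25 = 4.31 (L = 24); 15 × 27 × 7 / 365.25 = 7.76 (L = 12).
- F = 72: 15 × 39 × 7 / 365.25 = 11.21 (L = 24); 15 × 51 × 7 / 365.25 = 14.66 (L = 12).

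Expected uncounted events:
- F = 48: 4.31 × 0.005 = 0.02 to 7.76 × 0.02 = 0.16.
- F = 72: 11.21 × 0.005 = 0.06 to 14.66 × 0.02 = 0.29.

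Protocol 6.3 allows for subjects who reach Week 144 in the double-blind period. Taking F = 144 and L = 12 for all 15 as an extreme: 15 × 123 × 7 / 365.25 = 35.4 person-years, or 0.18 to 0.71 events, still below one.

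**4. What would one uncounted subject do?** With planned arms of 100 and 50 (Protocol 9.3): 1/100 = 1.0 percentage point for luspatercept; 1/50 = 2.0 points for placebo.

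**The case against.** The strongest reply is that this is a deliberate and consistent convention. SAP 11.1 analyses adverse events as TEAEs, and Protocol 9.7 plans TEAE summaries as well. Nothing is lost: a late case stands in listings sorted by arm with TEAEs flagged, late cases judged suspected are already in the table, and fatal ones reach the table of deaths. With a fraction of one event expected, counting from a listing is easy. The 1.0 and 2.0 points apply only if an event occurs. At the upper value of 0.29 events, the expected shift is 0.29/150, about 0.2 points, and it is the same in each arm if 10% stop in each. Stoppers who withdraw consent, die or are lost to follow-up add little or no time outside the window.

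All of this stands, and it is why the point is minor. It does not remove the gap: a stated rule leaves collected cases of the SAP's only AESIs out of their one incidence table.

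A reader might infer more than the documents support:
- **A protocol–SAP contradiction.** There is none. The protocol sets what is collected and does not promise an all-events table.
- **A gap spanning the years of long-term follow-up.** This SAP uses data only up to its cutoff. Later events belong to the final report or the rollover study.
- **A table biased toward one arm.** Nothing in the documents shows that stopping or causality judgments will differ by arm.
- **A flawed time-to-first-AESI summary.** The event set is merely unstated.

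**Conclusion.** The point holds as a minor, cheap improvement. A non-fatal malignancy or premalignancy that starts more than 63 days after last dose and is judged not suspected is collected and listed by arm, but not counted in the by-arm AESI incidence table. Only subjects who stop treatment more than 63 days before cutoff are concerned, and the effect is purely descriptive. The expected number of uncounted events is well under one. That rests on the assumed stopping pattern, follow-up and event rate, none of which the documents supply; the number may well be zero. The reason to act is the low cost and the special status of these events, not a large expected count.

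**What to change.** Keep the TEAE table. Add to SAP 11.2 one by-arm table, in the safety population by treatment received, of all malignancy and premalignancy events from first dose to data cutoff, irrespective of TEAE window and causality. Show n (%) together with total follow-up time per arm, or a rate per person-year: off-treatment follow-up may differ between arms, and a crude percentage alone would then be hard to interpret. While editing, one sentence should say which event set time to first AESI uses.

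The cost is one extra descriptive table from data already collected and listed. The reported AESI count may rise.
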